The study we are proposing has the potential to influence the way treatment of PTSD and alcohol dependence is delivered across the VA Healthcare Administration (VHA) and the Department of Defense. The population we are going to study are veterans that have served in the military and may have participated in past or current military conflicts. All participants will have current Diagnostic and Statistical Manual of Mental Disorder, 4th Edition (DSM-IV) diagnoses of PTSD and alcohol dependence, two of the most common diagnoses among veterans particularly those who have experienced combat.

Currently Cognitive Processing Therapy (CPT) and CPT-C (CPT without imaginal exposure) are being rolled out nationally in a large dissemination project by the Veterans Health Administration (VHA) and the Department of Defense (DoD) as one of two gold standards for the treatment of PTSD. Unfortunately, neither CPT nor CPT-C address the needs of patients with comorbid alcohol dependence. Our study will further test a newly developed enhanced CPT-C (E-CPT-C) for veterans with PTSD and comorbid alcohol dependence. The study will test E-CPT-C in combination with a new pharmacotherapy for veterans with PTSD and alcohol dependence. Zonisamide is a promising new pharmacotherapy for alcoholism. If effective, it has the potential to be prescribed as a first line medication for alcoholism for veterans.

Overview:

This is a randomized, controlled trial with 100 veterans diagnosed with PTSD and comorbid alcohol dependence. Veterans will be randomized to receive either zonisamide (400 mg) or placebo for 12 weeks in a double blind fashion. Randomization will be done using 3:1 ratio and will be performed by our research pharmacy using a random assignment in blocks of 4- 3 will be assigned to active medication and 1 to placebo.. Medication will be titrated over a 6 week titration phase followed by a 6 week treatment phase. All veterans will receive E-CPT-C therapy for the 12 weeks of treatment; E-CPT-C will be provided by trained and qualified clinicians with extensive experience providing E-CPT-C. Veterans will be recruited primarily through advertisement, but also through the clinical facilities at the VA and from other collaborators.

Experimental subjects:

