The target sample is 100 veterans diagnosed with PTSD and comorbid alcohol dependence. Veterans will be recruited from: 1) advertisement, 2) from PTSD clinics and patient units at VA Connecticut Healthcare System (VACT), and 3) from the group of patients entering treatment for alcohol use disorders at VACT Substance Abuse Treatment Program. We will review existing medical records to identify potential participants. Outreach will also be conducted to local Veteran Centers, where staff from VACT consults. The PTSD staff has also been involved in outreach to the community for returning OIF/OEF veterans. Each veteran will be carefully screened and assessed using the inclusion and exclusion criteria found above in Section 8.

X. Informed Consent Process

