Initial assessment will include the following measures: (1) Alcohol Dependence Scale (ADS) (Skinner and Allen 1982) is a self-report measure of alcohol dependence consisting of 25 items and will be used to measure the degree of dependence and control for possible group differences in alcohol dependence. (2) Clinical Institute Withdrawal Assessment Scale (CIWA, Ar) (Sullivan et al 1989) is an interviewer driven measure of alcohol withdrawal consisting of 10 items rated on a scale from 0 to 7 and will be used to rule out withdrawal symptoms requiring medical treatment. (3) Demographic information will be collected including contact information and self-designated racial and ethnic data, in accordance with National Institute of Health guidelines.

Study Assessments will include the following: (all measures – except the CAPS which will be used every two weeks - will be administered on each study visit, every week).

(a) The Timeline Follow-Back (TLFB) method (Sobell and Sobell 1992) will be used to document the degree of daily alcohol consumption and to monitor the use of other substances during 12 weeks of treatment.

(b) Obsessive-Compulsive Drinking Scale (OCDS) (Anton et al 1995) will be used to measure alcohol craving throughout the study. The OCDS consists of two subscales and measures obsessive and compulsive thoughts related to drinking.

(c) Clinicians Administered PTSD Scale (CAPS) will be used to obtain data on the frequency and severity of PTSD symptoms and will be administered every two weeks.

(d) Hamilton Depression Scale (HAMD) (Hamilton 1960) will be used to assess the degree and severity of depressive symptomatology. Given the overlap of PTSD and depression this scale will serve as another measure of psychiatric symptomatology.

(e) Posttraumatic Stress Disorder Checklist (PCL-C) will be used to measure PTSD symptoms every week on each visit. The PCL-C is a self-report scale that shares similar

reliability with the CAPS. (Weathers et al 1996)

(f) Modified Version of the Systematic Assessment for Treatment Emergent Events (SAFTEE) will be used to collect information on emergent side effects and their severity (weeks 1-12). This modified version will include, among other side effects, symptoms associated with zonisamide including: fatigue, decreased appetite, dizziness, headache, nausea, and agitation/irritability.

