Table 1. Summary of Weekly Study Assessments

Assessments	0	1	2	3	4	5	6	7	8	9	10	11	12	13	14	25
SCID I	x															
TLFB	x	x	x	x	x	x	x	x	x	x	x	x	x	x	x	x
OCDS		x	x	x	x	x	x	x	x	x	x	x	x	x	x	x

ADS	x														
Demographics	x														
CIWA	x														
CAPS Dx	x														
CAPS Sx		x		x		x		x		x		x		x	x
HAMD		x	x	x	x	x	x	x	x	x	x	x	x	x	x
PCL-C		x	x	x	x	x	x	x	x	x	x	x	x	x	x
SAFTEE		x	x	x	x	x	x	x	x	x	x	x	x	x	x
Independent Psychiatric Exam	x														
Physical Examination	x														
Medication Count		x	x	x	x	x	x	x	x	x	x	x	x	x	x
EKG	x														
Medical History	x														
Labs	x				x			x				x			x
UTOX	x	x	x	x	x	x	x	x	x	x	x	x	x	x	x

Data Analysis:

Descriptive statistics and graphs will be used to summarize the data on all randomized veterans. All continuous variables will be examined for adherence to the normal distribution using normal probability plots and Kolmogorov-Smirnov tests. Transformations will be applied if needed. If normality is not satisfied and transformations do not help with achieving normality alternative analytic strategies will be considered such as generalized estimating equations (GEE) or nonparametric methods for repeated measures analysis (Brunner et al 2002). For the primary hypotheses we will use mixed effects models to assess change in alcohol consumption and craving over time. Study medication (zonisamide vs placebo) and time (in weeks and months) will be used as a within-subject factors. The primary outcome drinking variable will be heavy drinking days and drinks per week calculated from the timeline data.

If significant differences between groups are observed Bonferroni adjusted post-hoc tests will be performed to test group differences at each time point. The same model will be used to examine changes in craving (using the OCDS) and PTSD symptoms (using the PCL every week and the CAPS every two weeks) over time.

XII. Labeling and Storage of Data and Specimens

All data and blood specimens will be stored without direct identifiable information, but will be identifiable via a linking code. Blood will not be used for the purpose of establishing cell lines. Any hard copy records associated with the study will be kept in locked offices. The secured research records are labeled with code numbers only (names and other identifying information are kept separate from research records). Access to hard copy data is only given to

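### Holm's step-down adjustment could replace plain Bonferroni for the post-hoc time-point comparisons: same error control, some lost power back, primary analysis untouched

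*Combined protocol and SAP*

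**What the plan says.** The Data Analysis part of Section XI gives the main inference to a longitudinal model: "For the primary hypotheses we will use mixed effects models to assess change in alcohol consumption and craving over time". It adds that "time (in weeks and months) will be used as a within-subject factors". The comparisons at single time points come afterwards and are conditional: "If significant differences between groups are observed", then "Bonferroni adjusted post-hoc tests will be performed to test group differences at each time point". The same model is to be used for craving and for PTSD symptoms.

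The plan does not state the number of comparisons, the family alpha, or whether the family spans outcomes. The number can only be inferred. In the Study Assessments list, the drinking calendar "will be used to document the degree of daily alcohol consumption and to monitor the use of other substances during 12 weeks of treatment", which gives 12 weekly points. Table 1 also marks the drinking calendar and the craving scale at weeks 13, 14 and 25, which gives 15 post-baseline visits. The clinician-rated PTSD scale "will be administered every two weeks", so its family is smaller. No stepwise adjustment is mentioned.

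**The concern.** With 12 to 15 comparisons, Bonferroni holds every week to a threshold of 0.05/12 or 0.05/15, even after other weeks have clearly separated. Holm starts at the same threshold and relaxes it as weeks are rejected, with no loss of familywise error control. Keeping plain Bonferroni therefore gives up some ability to describe which weeks differ. At 3:1 allocation the placebo arm has at most 25 patients, so weekly comparisons have little power to spare. What is at stake is how fully the weekly pattern is described once a group difference has been found.

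**Working it through.** The plan states no power or alpha for these tests, so there is no figure of its own to reproduce.

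**Inputs from the documents**
- Allocation (Section VII, Overview): "Randomization will be done using 3:1 ratio".
- Sample size (Section IX): "The target sample is 100 veterans diagnosed with PTSD and comorbid alcohol dependence", hence 75 against 25. The Experimental subjects paragraph in Section VII says fifty, hence 37.5 against 12.5 on average; this is run as a sensitivity case.
- Family size m: 12 or 15, inferred as above.
- Titration (Medication Treatment): 100, 200, 200, 300, 300 mg in weeks 1 to 5, then 400 mg.

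**Assumed, because the documents are silent**
- Two-sided family alpha 0.05.
- Standardised effect d of 0.5 or 0.7 SD, with 0.3 and 0.8 as outer cases.
- Equal correlation between weeks of 0.5 to 0.7, and no dropout.

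**Thresholds.** Bonferroni rejects when p ≤ 0.05/m, which is 0.00417 for m = 12 and 0.00333 for m = 15. Holm orders the p-values and rejects the i-th smallest while p(i) ≤ 0.05/(m − i + 1). For m = 12 its thresholds run 0.05/12 = 0.00417, 0.05/11 = 0.00455, and so on up to 0.05. The first step is identical to Bonferroni and each later step is looser.

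**Bonferroni rate by formula.** The weekly z statistic has mean d × √(n₁n₂/(n₁+n₂)). For 75 and 25, √(75 × 25/100) = 4.330. The two-sided critical value is 2.865 for m = 12 and 2.935 for m = 15.
- d = 0.5: mean 2.165; Φ(2.165 − 2.865) = 24%; for m = 15, Φ(2.165 − 2.935) = 22%.
- d = 0.7: mean 3.031; Φ(3.031 − 2.865) = 57%; for m = 15, Φ(3.031 − 2.935) = 54%.
- 50 patients, d = 0.5: √(37.5 × 12.5/50) = 3.062, mean 1.531; Φ(1.531 − 2.865) = 9%.

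**Holm by simulation.** Each scenario used 40,000 sets of correlated normal z statistics. The table gives the average chance of flagging a week that has an effect, Bonferroni to Holm.

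| Scenario | d = 0.5 | d = 0.7 |
|---|---|---|
| N = 100, 12 weeks, constant effect | 24% to 30-31% | 57% to about 68% |
| N = 100, 15 visits, constant effect | 22% to 27-29% | 54% to 65-66% |
| N = 100, 12 weeks, effect proportional to titrated dose | 17% to 20% | 39% to 46% |
| N = 100, 12 weeks, effect only from week 6 | 24% to 26-27% | 56-57% to 60-61% |
| N = 50, 12 weeks, constant effect | 9% to 11-12% | – |

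The outer cases used N = 100, a constant effect, m from 12 to 15 and correlation 0.3 to 0.7. At 0.3 SD the rate goes from 5-6% to 6-8%; at 0.8 SD, from 70-73% to 81-85%.

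**Share of the loss recovered.** An unadjusted 5% test at d = 0.5 would flag a week with chance Φ(2.165 − 1.960) = 58%. Bonferroni loses 58 − 24 = 34 points and Holm returns 6 to 7 of them, about a fifth. At d = 0.7 the unadjusted rate is Φ(3.031 − 1.960) = 86%. The loss is 86 − 57 = 29 points and Holm returns about 68 − 57 = 11, somewhat under two fifths.

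**Any week at all.** The chance of at least one significant week is the same under both methods in every scenario: for example, 71.1% and 71.1% at d = 0.5, correlation 0.5, m = 12.

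**Error control.** With no effect anywhere, both methods had the same simulated familywise error: 3.7% at correlation 0.5 and 2.7% at 0.7. With an effect only from week 6, Holm's error stayed at or below 3.2%.

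**The case against.** The strongest reply is that nothing in the plan is wrong. Bonferroni is valid under any dependence, the tests are post-hoc and run only after a significant group difference, and the primary hypotheses rest on the mixed models. All of that stands. A reader might infer that the choice of Bonferroni weakens the primary analysis; it does not affect that test, its alpha or its power.

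A reader might also infer that these tests are how the trial establishes when the drug starts to work. The documents do not support that. No aim or hypothesis in the Research Objectives asks about onset, and the planned descriptive graphs would show the weekly pattern in any case.

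The larger gains depend on favourable assumptions: a full effect from week 1 although the dose is titrated, 100 patients although another paragraph says fifty, and effects of 0.5 SD or more. The rates in the table also ignore the requirement of a prior significant difference. If that requirement is modelled as a 5% test of the time-averaged difference, then at 0.5 SD with onset at week 6 and correlation 0.5 the rates are 20% to 22% instead of 24% to 27%. The family of 12 to 15 is inferred, is smaller for the biweekly scale, and could differ again if months are used.

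Finally, Bonferroni has simple matching simultaneous intervals and Holm does not. That cost is real but small. These points lower the stakes; they do not give a reason to prefer Bonferroni for the adjusted p-values.

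**Conclusion.** The point holds as an optional gain in efficiency. Holm gives the same strong familywise error control under any dependence and never rejects less. Under the stated assumptions the gain per week is about 6 to 7 percentage points at 0.5 SD and about 11 at 0.7 SD with 100 patients, 12 weeks and a constant effect. It falls to about 3 and 7 points if the effect follows the titration, and to 2 to 3 points at 0.5 SD with 50 patients. Every one of these figures depends on an effect size, correlation and alpha that the documents do not give.

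Two stronger readings should be resisted. The first is that Holm recovers the power Bonferroni loses: it recovers only part, and only after a first week has been flagged. The second is that Holm helps because the weeks are correlated: it makes no use of the correlation. A critical value built from the correlation (about 2.65 for m = 12 at correlation 0.7) would raise the chance of any finding from 58% to 67% at 0.5 SD, whereas Holm leaves it at 58%.

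The severity is the lowest: a cheap improvement, not a defect.

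**What to change.** In the Data Analysis text of Section XI, specify Holm adjustment in place of Bonferroni adjustment for the group comparisons at each time point. Report unadjusted confidence intervals beside the Holm-adjusted p-values and label them as unadjusted.

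The cost is a one-word change plus a sentence on the intervals. What is given up is the simple simultaneous interval that goes with Bonferroni. No data collection, sample size, primary model or alpha changes.
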